### Table 7Dose-Limiting Toxicities

Participants who withdraw from the study before completing DLT period for reasons other than DLT may be replaced. If a participant experiences a DLT during the DLT period of treatment, the participant will be discontinued from study treatment unless the investigator considers it in the best interest of the participant to continue on study (e.g., in case of symptomatic disease improvement, and/or if the DLT is viewed as preventable in subsequent doses/visits, etc.) and the sponsor approves of the decision.

Guidance for the management of toxicity, including dose modification algorithms, is provided in Section 6.4.

# 4.1.2. Dose Escalation Decisions

The Dose Escalation committee, in joint discussion with the participating investigators, will be responsible for determining whether cohort level dose escalation or de-escalation during the study should continue as recommended by the N-CRM approach for Part 1 and the mTPI approach for Part 2. Prior to the dose escalation/de-escalation decision, the medical monitor, clinical scientist, safety physician/scientist, clinical pharmacologist,

### CONFIDENTIAL

statistician, and investigators will review critical safety data defined in the Dose Escalation Plan, including data on all adverse events including non-DLT toxicities, laboratory assessments and other safety evaluations, as well as any available PK and/or PD data. The quality review of critical safety data will be described in the Dose Escalation Plan, which includes ongoing study monitoring visits along with data review of the clinical database.

The dose-escalation/de-escalation decision and rationale for each cohort will be discussed with investigators during teleconference(s) and documented in writing with copies maintained at each study site and in the GSK trial master file.

### Intra-patient dose escalation

In Part 1, participants are permitted to dose escalate between the 2-3 induction 5/2/5 q28d cycles based on discussion and agreement with Medical Monitor and the Investigator after reviewing available safety and laboratory data, and in line with the following safety and tolerability parameters:

- Investigator and MM must both consider that dose escalation is in the best interests of the participant
- Participant must have received at least 7 of the 10 doses in the prior cycle
- Participant must not have experienced:
  - $\circ$  Any Grade  $\geq$ 3 adverse event
  - $\circ$  Grade  $\geq$ 3 TLS
  - A DLT (which includes Grade 3 CRS, all non-hematologic Grade 3 events with a few exceptions as per Table 7)
  - More than 1 episode of Grade 2 CRS in the previous cycle
  - Evidence of ongoing immune related AEs during the observation period (sustained or intermittent Grade ≥2 fever ongoing after the first week of the observation period, in which infectious cause is ruled out).

# 4.2. Number of Participants

Approximately 22 participants may be enrolled in Part 1, and approximately 50 participants may be enrolled in Part 2. The total number of participants to be enrolled is an estimate and will depend on the number needed to adequately characterize the DLT and PD profile and determine the MTD(s)/RP2D(s). All participants who take at least one dose of study intervention will be considered evaluable for analysis. See the statistical considerations, Section 9.2, for justification of the sample size.

# 4.3. Scientific Rationale for Study Design

Preclinical data support the use of STING agonists for the treatment of AML. A study evaluating the effect of a STING agonist on 144 different cancer cell lines spanning 14 different histologies revealed that GSK3745417 induced cell growth inhibition in two out of two AML cell lines tested and one large cell lymphoma cell line. In a subsequent study focused on 12 additional AML cell lines, GSK3745417 induced cytotoxicity in 3 of 12 cell lines, cytostaticity in 5 of 12 cell lines, or modest to no effect in 4 of 12 cell lines.

Even with these "cytostatic" lines, apoptosis was induced. Over both studies, GSK3745417 induced cytotoxicity or cytostaticity in 64% (9 of 14) of all AML cell lines tested. Mechanistically, GSK3745417 activates caspases 3/7 in highly sensitive AML cell lines, suggesting a role for STING mediated apoptosis in driving AML cell death. In addition to STING driven cytotoxicity or cytostaticity of AML, a recent publication also suggests STING agonists stimulate potent anti-AML immunity in a mouse model via induction of type I interferons and proinflammatory cytokines (Curran, 2016). A 5/2/5 q28d dosing regimen is being evaluated in Part 1 since it is hypothesized that increased dosing frequency, and therefore average concentration, of GSK3745417 will enhance the direct cell killing effect.

The proposed Phase 1 study will evaluate the safety and tolerability, PK, PD, and preliminary clinical activity of increasing doses of GSK3745417 administered IV in adult participants with relapsed or refractory AML or high-risk MDS and will determine a dose and schedule of GSK3745417 for future clinical studies.

# 4.4. Justification for Dose

# 4.4.1. Human Experience with GSK3745417 Dosing in Participants with Solid Tumors

For the ongoing first time in human study (Study 208850), the minimally anticipated biological effect level (MABEL) approach was used in conjunction with the ICH S9 guidance on selection of starting dose for a biopharmaceutical with immune agonistic properties to select a safe starting dose of GSK3745417 for use in cancer patients with advanced tumors with due consideration of relevant in vitro, ex vivo, and in vivo nonclinical data. A dose level of 100  $\mu$ g QW was used as a starting dose following a 10-fold safety factor from the identified MABEL dose of 1000  $\mu$ g and was tolerated in humans. The 100  $\mu$ g was considered safe and tolerated as no DLTs were observed during the DLT determination period of 21 days. To date, three dose levels (100, 200, and 400  $\mu$ g) have been investigated in the solid tumor population, with further detail in the human PK section below. MTD was identified as 400 ug for Q1W mono therapy. Study 208850 is ongoing with further investigations into Q3W dosing of GSK3745417 monotherapy, and eventually Q1W or Q3W in combination therapy with dostarlimab.

### 4.4.2. Selected Human Starting Dose and Discussion

It is unclear how the observed solid tumor effects of GSK3745417 in BALB/c mice will translate into the human AML disseminated tumor setting or the current human experience in solid tumors, though it is noted that the  $C_{max}$  in the 200 and 400 µg dose levels in human approximates the 3 h concentration in the BALB/c tumor model where tumor regression was observed. Regarding the direct cell killing mechanism, to match the geometric mean of the gIC50 values of 5.14 ng/mL for growth inhibition, and assuming linear PK, a predicted dose level of ~16 µg would be required to achieve a  $C_{max}$  of ~5.14 ng/mL.

Therefore, with the lower dose goal of achieving direct cell killing, the recommended starting dose in the AML population is 12.5  $\mu$ g, which is approximately 1× of the geometric mean of the gIC50 in AML cell lines, 1/8th of the lowest dose studied to date in the solid tumor population (Study 208850), and 1/16nd of the maximum tolerated dose in the solid tumor population (Study 208850). The 100-µg starting dose in the solid tumor study was dosed weekly; 12.5 µg daily for 5 days is still cumulatively a lower dose than the 100-µg single dose used in the solid tumor study. This starting dose would be predicted to result in a Cmax of ~4 ng/mL and an AUC of ~8 hr\*ng/mL. This approach relies on the finding in bone marrow that the AML population would have no higher cytokine induction through the innate immune system response, and therefore represents an additional three low-dose cohorts compared to the solid tumor study (Study 208850). This low starting dose of 12.5 µg also provides an important safety margin given the preliminary non-clinical data which suggest that there may be some accumulation of cytokine related symptoms/immune system activation with daily dosing. Given the available safety profiles with human dosing in 21 participants in Study 208850, and absence of significant cytokine related symptoms at the starting dose of 0.1 mg in Study 208805 this would appear to be a reasonable risk/benefit trade-off because of the potential benefit of cell killing at lower dose levels.

# 4.5. End of Study Definition

The end of the study is defined as the date of the last visit of the last participant in the study or last scheduled procedure shown in the Schedule of Activities (SoA) for the last participant in the trial globally.

A participant is considered to have completed the study if he/she has completed all phases of the study including the last visit or the last scheduled procedure shown in the Schedule of Activities. In addition, if the sponsor decides to close the study, participants who are receiving study intervention or are in the follow-up period will be considered to have completed the study.

Participant would be considered off study in the event of death, withdrew consent, or lost to follow-up.

# 5. STUDY POPULATION

Prospective approval of protocol deviations to recruitment and enrollment criteria, also known as protocol waivers or exemptions, is not permitted.

# 5.1. Inclusion Criteria

Participants are eligible for inclusion in this study if all the following criteria apply:

1. Must be  $\geq 18$  years of age and  $\leq 75$  years of age at the time of signing the informed consent for dose escalation and  $\geq 18$  years of age at the time of signing the informed consent for the dose expansion.

- 2. Capable of giving signed informed consent which includes compliance with the requirements and restrictions listed in the informed consent form (ICF) and in the protocol.
- 3. Eastern Cooperative Oncology Group (ECOG) performance status of 0 or 1.
- 4. Participants with AML/High Risk MDS are eligible for participation in Part 1 and Part 2 if they have:
  - A diagnosis of AML according to the World Health Organization 2016 criteria (Arber, 2016) with relapsed or refractory disease and ineligible for or have exhausted standard therapeutic options.
  - Have high-risk or high/very high by IPSS-Revised [IPSS-R] criteria [Greenberg] MDS (restricted to Part 1) that has relapsed after or been refractory to prior therapy with hypomethylating agent.

5.	Adeq	uate	organ	function:	
----	------	------	-------	-----------	--

Organ system	Laboratory Values	
Hematologic		
White blood cell count (absolute)	≤25,000/µL (both at screening and prior to study drug administration on Day 1) (hydroxyurea is permitted to reduce white cell count prior to screening). Hydroxyurea or leukapheresis may be used prior to and throughout study to control white cell count	
PT/INR and PTT in patients not receiving therapeutic anticoagulants	≤1.5 x ULN	
PT/INR and PTT in patients receiving therapeutic	Within the intended therapeutic range of the	
anticoagulants	anticoagulant	
Hepatic		
Total bilirubin	≤1.5 x ULN	
For participants with Gilbert's Syndrome (only if	$\leq 3.0 \times ULN$	
direct bilirubin 🛛 35%)		
ALT	≤2.5 x ULN	
Renal		
eGFR by CKD-EPI	≥50mL/min/1.73m 	
Endocrine		
TSH 	WNL	
Cardiac		
Ejection fraction	≥Lower limit of normal (LLN) (minimum of 50%)	

 If TSH is not within normal limits at baseline, the participant may still be eligible if total T3 or free T3 and free T4 are within the normal limits

6. Participants with a prior history of stem cell transplant (autologous and/or allogeneic) are allowed if:
- No clinical signs or symptoms of graft versus host disease (other than Grade 1 GVHD (<25% skin surface affected) and the participant is off all systemic immunosuppression. (Note: topical steroids for G1 skin GVHD are permitted on study)
- 7. Agree to abide by the gender specific contraceptive requirements below:
  - Female participants are eligible to participate if they are not either pregnant or breastfeeding, and at least one of the following conditions applies:
    - $\circ$  Is not a woman of childbearing potential (WOCBP), or
    - Is a WOCBP and using a contraceptive method that is highly effective (with a failure rate of <1% per year), with low user dependency during the study treatment period and for at least 7 days after the last dose of study treatment and agrees not to donate eggs (ova, oocytes) for the purpose of reproduction during this period. The investigator should evaluate the effectiveness of the contraceptive method in relationship to the first dose of study treatment.

    - A WOCBP must have a negative highly sensitive pregnancy test (urine or serum) as required by local regulations) within 7 days before the first dose of study intervention. If a urine test cannot be confirmed as negative (e.g., an ambiguous result), a serum pregnancy test is required. In such cases, the participant must be excluded from participation if the serum pregnancy result is positive.
    - Additional requirements for pregnancy testing during and after study treatment will be described in the protocol.
    - The investigator is responsible for a review of medical history, menstrual history, and recent sexual activity to decrease the risk for inclusion of a woman with an early undetected pregnancy.
  - Male participants and WOCBP taking hydroxyurea during the study must follow contraceptive guidance in the hydroxyurea prescribing information

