# 4. STUDY DESIGN

# 4.1. Overall Design

This is a Phase 1 open-label study of intravenous GSK3745417 to evaluate safety, tolerability, pharmacokinetics, pharmacodynamics and determine RP2D and schedule in participants with relapsed or refractory acute myeloid leukemia (AML) and high-risk myelodysplastic syndrome (HR-MDS).

The study will be conducted in a staged approach consisting of 2 parts. Part 1 represents dose escalation to determine a cohort level MTD and incorporates intra-patient dose escalation within cohorts to minimize the potential for a participant to be exposed to a non-efficacious sub-therapeutic dose. Dosing in Part 1 will include 3 initial cycles followed by "maintenance" at a weekly dosing schedule. Part 2 represents an expansion cohort at the recommended induction dose/doses and schedule from Part 1 for 3 cycles, followed by either a weekly, every 3 weeks, or less frequent dosing schedule for "maintenance." Approximately 72 participants will be enrolled: approximately 22 participants in Part 1 and 50 participants in Part 2.

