Part 2: Efficacy will be evaluated after an induction phase in approximately 50 participants, 25 AML participants and 25 HR-MDS participants. The induction phase consists of a treatment regimen at the dose/doses determined to be safe in Part 1 (RP2D). The number of cycles, number of doses investigated in the induction phase, and/or dosing schedule of 5/2/5 q28d treatment will be determined and may be modified based on a review of safety and PK data generated from Part 1. After the induction phase, patients will continue to either a weekly (Q1W), every 3 weeks (Q3W), or less frequent dosing schedule for maintenance treatment, if a CR or PR is observed (See Response Criteria for Participants with AML Appendix 9; See IWG Criteria for Response for Participants with MDS Appendix 8). Participants with stable disease or PR after 3 induction cycles might receive additional cycles if the assessment by the investigator determined a benefit and GSK Medical Monitor agrees. Up to three dose levels for maintenance treatment will be evaluated in the maintenance dose escalation. The DLT period for the maintenance dose escalation portion of Part 2 will be 28 days starting at Day 1 of each cycle. Dose escalation for the maintenance schedule will start at the highest dose cleared for safety in Part 1. Part 2 will evaluate the efficacy of the induction regimen separately for AML and HR-MDS as well as the tolerability and duration of response of the Q1W or Q3W maintenance schedules to determine the best dose and schedule for further studies.

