# 8.5. Genetics and Pharmacogenomics

## 8.6. Biomarkers

# 9. STATISTICAL CONSIDERATIONS

# 9.1. Statistical Hypotheses

With respect to the primary objectives and endpoints of Part 1 and the maintenance dosing of Part 2, no specific statistical hypotheses are being tested. The primary focus of Part 1 and maintenance dosing of Part 2 will be on determining the RP2D for both induction and maintenance for further exploration based upon the safety, PK, and anticancer activity profiles of GSK3745417 alone.

The primary efficacy objective of the expansion cohort in Part 2 is to demonstrate that GSK3745417 is clinically active at the proposed induction RP2D(s) in participants with R/R AML and separately in participants with HR-MDS.

Specifically, the first half of Part 2 is designed to provide evidence with regards to ORR to support the null hypothesis:

H₀: p≤10%

or to reject it in favor of the alternative hypothesis:

HA: p≥30%

where p is the overall response rate.

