## Part 2:

Approximately 50 participants will be recruited for Part 2, 25 AML participants and 25 HR-MDS participants. Part 2 cohort expansion is designed based on predictive probability methodology of Lee and Liu (Lee, 2008). A test that the overall response rate [ORR] (p) is less than or equal to the null hypothesis rate versus the response rate is greater than or equal to the alternative rate is being performed separately in each indication using the stopping rules shown in Table 15.

For Part 2 the hypotheses in terms of overall response rate (p) are detailed below.

The null hypothesis is:

H0: p≤10%

The alternative hypothesis is:

HA: p≥30%

The null hypothesis of p=10% was specified given low likelihood of response following failure of standard therapies. The alternative hypothesis of  $p\ge30\%$  was specified to ensure robust evidence for efficacy to support advancement of a novel drug.

GSK3745417 will be evaluated for efficacy in approximately 13 to 25 participants with AML and separately in 13 to 25 HR-MDS participants in the expansion cohorts.

The futility evaluation will occur after 13 participants have completed induction and allow for a maximum number of 25 participants. This design will have a type I error rate ( $\alpha$ ) of 0.09 and a power of 0.88. A cohort (AML and/or MDS) can be terminated early for futility if the predictive posterior probability of the response rate greater than the null hypothesis of 10% being above 80% is very low, i.e., below 10% ( $\theta$ L) for this design. The type I error rate and power were derived by explicitly stating null and alternative
hypotheses of response rate, the minimum and maximum sample size, boundaries of predictive probability for futility criteria and the selection of the optimizing criterion as the maximization of power under the alternative hypothesis. The Bayesian prior used in determining the design was Beta (0.01, 0.09), a distribution with a mean response rate of 10%. Under the null hypothesis, that is, if the true response rate is less than 10%, the expected sample size of the design is 17.5 participants per cohort and probability of early termination is 62.1%. Under the alternative hypothesis, that is, if the true response rate is at least 30%, the expected sample size of the design is 24.2 participants and probability of early termination is 6.4%.

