### Table 15Stopping Rules for Part 2 Cohort Expansion

Number of Evaluable Participants a	Stop for Futility if No. of Responders Less Than or Equal to This Number b
13	1
25	4

a. Evaluable participants for response assessment are defined by any or all of the following criteria:

• Participants who have at least one post-baseline disease assessment.

• Participants who have progressed or have died or have withdrawn from study treatment due to any reason.

b. The specific criteria for stopping an expansion cohort due to futility. For instance, if 13 participants are enrolled, then the cohort may be stopped for futility if number of Responders ≤1.
Note: These rules will be applied to both AML and HP MDS cohorts in Part 2.

Note: These rules will be applied to both AML and HR-MDS cohorts in Part 2.

Enrollment into AML and/or HR-MDS cohorts in Part 2 may be stopped according to the rules in Table 15 once all enrolled participants in the expansion cohort have met criteria for evaluability (as defined in the footnote to Table 15) after induction. The futility stopping rules are intended as a guideline only. Actual decisions will depend on the totality of the data.

Up to 18 of these (AML and HR MDS) participants who respond to induction will continue to maintenance dosing. The maintenance dosing schedule will be determined based on data from the FTIH 208850 study. If enrollment into one of the cohorts (AML or HR MDS) is stopped early, additional participants in the other cohort may be enrolled to have a sufficient number of participants for maintenance dosing evaluation. Fewer doses in maintenance therapy are expected to be studied for dose escalation; therefore, the modified Toxicity Probability Interval (mTPI) procedure (Ji, 2013) (and not N-CRM) will be used to identify the MTD of GSK3745417 during maintenance dosing after 2 to 3 cycles of daily dosing at the induction MTD determined from Part 1. Part 2 will evaluate 3 increasing dose levels starting at the MTD determined from Part 1. The DLT period for Part 2 will be 28 days starting at Day 1 of each cycle. Dose escalation will target 3 participants up to a target maximum of 6 at each dose level. Dose escalation will proceed until the MTD for GSK3745417 in maintenance dosing is determined.

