## 9.4.3.3. Exploratory Biomarker Analyses

## 9.5. Interim Analysis

The primary driver for the dose-escalation decision(s) will be safety and tolerability of each dose cohort. For Part 1 induction and Part 2 maintenance, dose escalation and de-escalation decisions will be guided by an N-CRM model and mTPI, respectively. Predicted DLT rates will be provided with the aim of escalating to doses with small probability of excessive or unacceptable toxicity. Preliminary safety and available PK/PD data will be reviewed by the GSK study team and investigators after completion of each dose cohort. This review will support the decision on the dose level in the next dose cohort.

After the last cohort of participants completes the DLT observation period for induction in Part 1, a formal interim analysis will be performed to support the initiation of Part 2 and the recommended dose level for induction. Data considered to support these decisions will include, but are not limited to, safety, PK profile, PD, and observed signs of clinical activity. Details of the interim analysis will be provided in the SAP.

For Part 2, assessment of efficacy and safety will be performed after the first futility assessment based upon a minimum of 13 participants with available unconfirmed overall response data, separately for the AML and HR-MDS cohorts. If the stopping criteria for futility are met in either the AML or MDS cohort, further enrollment in that cohort may be stopped.

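### Inclusion criterion 4 restricts HR-MDS to Part 1, although its own lead-in and the Part 2 design plan an HR-MDS cohort of 25 with its own response-rate test

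*Protocol*

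**What the plan says.** Criterion 4 in Protocol Section 5.1 has a lead-in and two bullets. The lead-in is "Participants with AML/High Risk MDS are eligible for participation in Part 1 and Part 2 if they have". The first bullet covers relapsed or refractory AML. The second is the only route for MDS and is limited to "MDS (restricted to Part 1) that has relapsed after or been refractory to prior therapy with hypomethylating agent".

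The rest of the protocol treats HR-MDS as half of Part 2:

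- Section 1.1 (Synopsis) and Section 3 name HR-MDS in the primary efficacy objective of Part 2.
- Section 4.1: "Part 2 will evaluate the efficacy of the induction regimen separately for AML and HR-MDS".
- Section 4.1, on numbers: "Approximately 72 participants will be enrolled: approximately 22 participants in Part 1 and 50 participants in Part 2".
- Section 9.1 aims to show that the drug is "clinically active at the proposed induction RP2D(s) in participants with R/R AML and separately in participants with HR-MDS".
- Section 9.2: "Approximately 50 participants will be recruited for Part 2, 25 AML participants and 25 HR-MDS participants".
- The note to Table 15: "These rules will be applied to both AML and HR-MDS cohorts in Part 2".
- Section 9.5 plans the first futility assessment "based upon a minimum of 13 participants with available unconfirmed overall response data, separately for the AML and HR-MDS cohorts".

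The opening of Section 5 does not permit prospective approval of deviations from the recruitment and enrolment criteria. The SAP does not address the conflict, and its version history ties every version to protocol version 1.0.

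**The concern.** An HR-MDS candidate for Part 2 is admitted by the first line of criterion 4 and excluded by its second bullet. Limiting the parenthesis to that one bullet does not help: Part 2 would then have no MDS entry definition at all, because there is no other MDS bullet. Nor can a site safely treat the parenthesis as stray text. Criterion 1 also sets different rules for escalation and expansion (an upper age limit applies in escalation only), so part-specific limits are to be expected in this list.

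At stake is whether one of the two separately tested Part 2 populations can be enrolled. A site that follows the parenthesis enrols no HR-MDS participant. A site that follows the lead-in enrols people who fail a listed criterion, which is an eligibility deviation. If sites differ, HR-MDS enrolment depends on the site's reading and the eligibility of those enrolled is open to dispute.

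**Working it through.** **1. Is the conflict real?** The relevant statements, side by side:

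| Place in protocol | HR-MDS in Part 1 | HR-MDS in Part 2 |
|---|---|---|
| 5.1, criterion 4, lead-in | yes | yes |
| 5.1, criterion 4, MDS bullet | yes | no |
| 1.1 and 3, Part 2 primary objective | – | yes |
| 4.1, Part 2 | – | yes, 25 participants |
| 9.1, hypotheses | – | yes, separate aim |
| 9.2 and Table 15 | – | yes, 25 participants, own test and rule |
| 9.5, interim analysis | – | yes, separate look |

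Only the MDS bullet keeps HR-MDS out of Part 2. No passage in either document reconciles it with the rest.

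**2. Do the Part 2 design figures hold if the lead-in governs?** Inputs from Section 9.2 and Table 15, per cohort: first look at 13 participants, maximum 25; stop if 1 or fewer of 13 respond; not successful if 4 or fewer of 25 respond; null rate 0.10, alternative rate 0.30.

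The exact binomial formulas, with p the true response rate, are:

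- Early termination: PET = (1−p)^13 + 13·p·(1−p)^12
- Expected size: E[N] = 13·PET + 25·(1−PET)
- Probability of success: the sum over x = 2 to 13 of P(X₁ = x)·P(X₂ ≥ 5−x), with X₁ ~ Bin(13, p) and X₂ ~ Bin(12, p)

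At p = 0.10:

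- PET = 0.9^13 + 13(0.1)(0.9^12) = 0.6213
- E[N] = 13(0.6213) + 25(0.3787) = 17.54
- Success probability (type I error) = 0.0875

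At p = 0.30:

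- PET = 0.7^13 + 13(0.3)(0.7^12) = 0.0637
- E[N] = 13(0.0637) + 25(0.9363) = 24.24
- Success probability (power) = 0.8795

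| Quantity | Stated in 9.2 | Recomputed |
|---|---|---|
| Type I error | 0.09 | 0.0875 |
| Power | 0.88 | 0.8795 |
| Early termination, null | 62.1% | 62.1% |
| Early termination, alternative | 6.4% | 6.4% |
| Expected n, null | 17.5 | 17.5 |
| Expected n, alternative | 24.2 | 24.2 |

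Everything reproduces. The design arithmetic is sound, and the fault lies in the eligibility text alone.

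**3. What does each reading of criterion 4 give?**

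| | Lead-in applied | Parenthesis applied |
|---|---|---|
| HR-MDS in Part 2 | up to 25 | 0 |
| HR-MDS response-rate test | as planned | cannot be run |
| Part 2 total | 25 + 25 = 50 | 50 − 25 = 25 |
| Study total | 22 + 50 = 72 | 22 + 25 = 47 |

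The protocol gives all totals as approximate. The right-hand column is before any extra AML enrolment. Section 9.2 lets one cohort be enlarged for maintenance evaluation if the other is stopped early, and it does not say whether that covers a cohort that never opens.

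**The case against.** The strongest argument is that nothing now turns on this. SAP Section 4.8 says the study was terminated just as Part 1 finished recruitment and that nobody will be recruited to Part 2. Both readings admit HR-MDS to Part 1, the only part that ran. No participant, estimate or report output depends on the parenthesis. That is correct and limits the realised harm to nil. It does not correct the approved protocol.

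Second, the intent can be inferred. The lead-in and every Part 2 passage include HR-MDS, against one short parenthesis that looks like a drafting remnant. This makes deletion the more likely correction, but sites work from the criterion as written, and neither document says which wording was meant.

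Third, there was time to catch it. Section 9.5 requires a formal interim analysis before Part 2, and a bar on waivers does not bar an amendment. This also stands. It means that the conflict could have been repaired, not that it had been.

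Finally, reproducing the operating characteristics does not bear on the defect. That is fair. Its only use is to show that the correction need not touch the design.

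**Conclusion.** The concern holds. Criterion 4 contradicts itself, and its MDS bullet contradicts the Part 2 objectives, hypotheses, sample size, stopping rules and interim plan. Applied as written, the bullet leaves the HR-MDS efficacy question with 0 of 25 planned participants, halves Part 2 from about 50 to about 25, and lowers the study total from about 72 to about 47. This goes beyond a clerical slip, because it decides whether one of two separately tested populations can be enrolled, and sites have no waiver route around it. For the protocol as approved it must be corrected.

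The size rests on two assumptions: that a site applies the parenthesis literally, and that AML enrolment is not increased to compensate. No collected data are affected, because Part 2 did not open.

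**What to change.** Reconcile criterion 4 with the Part 2 passages by amendment before any Part 2 enrolment, or before the text is reused. The sponsor must state which was intended.

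- **(a) HR-MDS was meant to enter Part 2.** Delete the parenthesis from the MDS bullet. Criterion 4 then agrees with its lead-in and with Sections 1.1, 3, 4.1, 9.1, 9.2 and 9.5. No sample size or operating characteristic changes. All the other Part 2 text supports this option.
- **(b) The restriction was meant.** Correct the lead-in and remove the HR-MDS cohort, its hypothesis test and its futility rule from Part 2. Restate Part 2 as about 25 and the total as about 47, before any extra enrolment for maintenance. This means editing Sections 1.1, 3, 4.1, 4.2, 9.1, 9.2 (with Table 15) and 9.5, and the planned totals repeated in SAP Section 5.

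Under Section 10.1.1, either route needs ethics committee approval before implementation, and health authority approval if the amendment is substantial. Option (a) costs a wording change plus those approvals. Option (b) also means rewriting the Part 2 design.
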